9 ADVERSE EVENTS

The investigator and study staff are responsible for detecting and recording AEs and SAEs, during scheduled safety evaluations and whenever such information is brought to their attention.

This section of the protocol provides definitions and detailed procedures to be followed.

During each visit, the investigator will question the subject about adverse events using an open question taking care not to influence the subject's answers. Throughout the course of the study, every effort must be made to remain alert to possible AEs. If an AE occurs, the first concern should be for the safety of the subject. If necessary, appropriate medical intervention should be provided. At the signing of the ICF, each subject must be given the names and telephone numbers of study site staff in the ICF for reporting AEs and medical emergencies.

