7.9 Handling of Data after Rescue

For this study reporting, any data collected at and after rescue visits will not be used for the analyses and summary tables but will be included in the listings. This applies to both efficacy and safety tables as well as concomitant medication tables. The only exception is that adverse events collected at and after rescue visits will be summarized separately as described in Section 14.1.

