14 SAFETY ANALYSES

14.1 Adverse Events

Adverse events will be coded using Medical Dictionary for Regulatory Activities (MedDRA) version 26.1.

Treatment-emergent adverse events (TEAEs) are defined as any adverse events that occur during or after the Day 1 injections, or any adverse events that are continuous from the screening but worsen during or after the Day 1 injections.

Ocular and non-ocular TEAEs will be summarized separately. Summary of ocular TEAEs will be separated by study eye and non-study eye.

An overall summary including the number of events and the number and percentage of subjects who experienced at least one TEAE will be presented by treatment group and overall. The overall summary will also include at least one serious TEAE, treatment-related TEAE, treatment-related serious TEAE, TEAE leading to subject discontinuation from the study, and TEAE leading to death.

TEAEs will be summarized by System Organ Class (SOC) and Preferred Term (PT). Subjects are counted only once under each SOC or PT for which they have at least one TEAE.

Summaries by relationship to study product, by relationship to study procedure and by maximum severity will also be provided.

Serious TEAEs will not be summarized in table format as it is anticipated number of serious TEAEs will be very limited.

In addition, the following AE summaries will be provided for AEs collected at and after rescue visits:

- Overall summary of TEAE
- TEAE by SOC and PT

For these summaries, denominators to be used for percentage calculation will be number of Rescued subjects.

All AEs will be presented in a subject listing with a flag indicating TEAE and a flag indicating AEs occurred at and after rescue visits. In addition, all serious AEs will be presented in a separate listing.

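### SAP 7.9 and 14.1 split adverse events at rescue by when they were collected, not by onset, so an event that began before rescue surgery can leave the main TEAE tables

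*SAP*

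**What the plan says.** - **General rule, SAP 7.9.** After rescue, "any data collected at and after rescue visits will not be used for the analyses and summary tables"; the records stay in the listings. On scope: "This applies to both efficacy and safety tables as well as concomitant medication tables".
- **Exception for AEs, SAP 7.9.** "The only exception is that adverse events collected at and after rescue visits will be summarized separately as described in Section 14.1".
- **Post-rescue tables, SAP 14.1.** "the following AE summaries will be provided for AEs collected at and after rescue visits". There are two, an overall TEAE summary and a SOC/PT table, and the "denominators to be used for percentage calculation will be number of Rescued subjects". No post-rescue table by maximum severity or by relationship is planned.
- **Listing, SAP 14.1.** Each AE carries "a flag indicating AEs occurred at and after rescue visits". The criterion here is occurrence, not collection.
- **Other AE timing rules.** The TEAE definition (SAP 14.1) goes by occurrence relative to the Day 1 injection. The Month 6 cut-off (SAP 7.1) goes by AE start.
- **How AEs reach the record, Protocol 9.** "During each visit, the investigator will question the subject about adverse events using an open question". The same section also has staff record AEs whenever they learn of them by other routes.
- **Rescue timing.** Neither document defines a rescue visit, and none appears in the Schedule of Assessments. SAP 14.3 does use a rescue date, for time to rescue.

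**The concern.** The split should keep events that follow keratoplasty apart from events that follow the study injection. For BCVA or CCT a visit-based cut-off does this, because the collection date is the measurement date. AEs are different: a visit picks up whatever has begun since the last contact. A cut-off on collection therefore places an event by when the site heard of it, not by what the subject had been exposed to when it began.

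At stake is the safety comparison between arms, which is the secondary objective. Rescue follows decline in the study eye (Protocol 8.3), so any displacement would tend to concentrate in arms with more rescue. A displaced event leaves the tables by maximum severity and by relationship. Protocol 10.8 plans those summaries for TEAEs without a rescue exclusion. Changes in intensity are entered as separate records (Protocol 9.4.1). If an AE worsens before rescue and the new record is made at the rescue visit, the main severity table may keep only the milder record.

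**Working it through.** The plan states no figure on this point, so there is none to reproduce. The check is textual, with simple arithmetic on the schedule and arm size.

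**1. One event under each rule.** Inputs (illustrative record): injection Day 1; Month 3 visit Day 90; onset Day 110; rescue at the Month 4.5 visit, Day 135, where the event is first recorded.

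| Rule | Where used | Result |
|---|---|---|
| Collected at or after the rescue visit | SAP 7.9 and 14.1 tables | 135 ≥ 135: post-rescue table, out of the main tables |
| Occurred at or after the rescue visit | SAP 14.1 listing flag | 110 < 135: not flagged |
| Occurred after the Day 1 injection | SAP 14.1 TEAE definition | 110 > 1: TEAE |

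So the event is a TEAE, sits in the post-rescue table, and carries no post-rescue flag in the listing.

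**2. Dependence on what a rescue visit is.** If it is the day of surgery and an earlier evaluation visit recorded the event, the event stays in the main tables. If it is the evaluation visit itself, the event moves, and so does anything recorded between evaluation and surgery. The text allows either reading.

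**3. How long before rescue such an event could have begun.** This is the gap from the previous scheduled visit, without the optional Month 2 visit. Maximum gap = (later day + window) − (earlier day − window).

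| Interval | Nominal days | Maximum days |
|---|---|---|
| Week 4 to Month 3 | 90 − 30 = 60 | 97 − 23 = 74 |
| Month 3 to 4.5 | 135 − 90 = 45 | 149 − 83 = 66 |
| Month 4.5 to 6 | 180 − 135 = 45 | 194 − 121 = 73 |
| Month 6 to 9 | 270 − 180 = 90 | 284 − 166 = 118 |
| Month 9 to 12 | 360 − 270 = 90 | 374 − 256 = 118 |

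These are upper bounds on the interval. They say nothing about how many events fall in it.

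**4. Effect per subject moved.** With n = 20 per arm (SAP 4.1), R rescued subjects, and j subjects whose only event of a term is moved, the main table falls by j/20 and the post-rescue table gains j/R. Assume 6 of 20 have the term with onset before rescue, and R = 4; the documents supply neither number.

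| Allocation | Main table | Post-rescue table |
|---|---|---|
| By onset | 6/20 = 30% | 0/4 = 0% |
| By collection, j = 1 | 5/20 = 25% | 1/4 = 25% |
| By collection, j = 2 | 4/20 = 20% | 2/4 = 50% |

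For j = 1, the post-rescue figure runs from 1/2 = 50% at R = 2 to 1/6 = 16.7% at R = 6.

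**5. Partial onset dates.** SAP 7.11 imputes dates to flag treatment emergence and concomitance. A missing day becomes the first of the month, or the dose day in the month of dosing. When the month is also the month of rescue and rescue falls later in it, the imputed onset is always before rescue. An onset split that used this rule unchanged would place every such event in the main tables.

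**The case against.** The strongest reply is that the sponsor probably meant onset. The listing flag in the same section goes by occurrence, as does the TEAE definition, and the Month 6 cut-off goes by AE start. This makes onset a plausible intention. It does not settle the tables, because 7.9 and the 14.1 table text both say *collected*, and a programmer cannot satisfy both that wording and the flag.

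Other objections limit the size, and they stand:

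- AEs may be recorded between visits (Protocol 9), and SAEs are reported within 24 hours of site awareness (Protocol 9.5).
- Evaluation and consultation with the Medical Monitor precede rescue (Protocol 8.3), and unscheduled visits may include AE assessment (Protocol 8.4.12). Many events may therefore be on record before the day of surgery.
- Findings that only reflect the product not working are not AEs (Protocol 9.3). Some of what accompanies a failing eye is outside the AE tables under any rule.
- Moved events still appear in the two post-rescue tables and in the listings. No formal safety tests are planned (Protocol 10.8).

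A reader might infer that the visit gaps give the share of events misplaced, for example 60 of 90 days (67%) for rescue at Month 3. They do not: a share of calendar time is not a share of events, and that reading needs AEs to be recorded only at visits. A reader might also infer a bias of known size against particular arms. Without a rescue rate or AE timing by arm, the documents support a direction of risk but no amount.

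**Conclusion.** The concern holds as a defect in the allocation rule. Followed as written, SAP 7.9 and 14.1 move AEs with onset before rescue surgery into the post-rescue summaries when they are first recorded at the rescue visit, and the table and listing flag can classify the same event differently. The loss is confined to the main TEAE, maximum-severity and relatedness tables; no event disappears from the report.

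The only size that the documents support is the unit effect of 5 percentage points per subject moved, at about 20 per arm and where that subject has no other event of the term in the main table. The number moved could be near zero if evaluation visits routinely capture events before a surgery-day rescue visit. That the main tables materially understate harm is therefore possible, but not shown.

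**What to change.** Use one rule in SAP 7.9, the 14.1 tables and the 14.1 flag:

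1. AEs, including separate records for worsening, with onset on or after the rescue surgery date are post-rescue. All other TEAEs stay in the main tables, whichever visit recorded them.
2. Define the rescue visit for data that are tied to visits, such as BCVA, CCT and IOP.
3. State the rule for onset on the day of surgery. The wording in item 1 makes such events post-rescue by default, so say whether an event known to precede the operation that day is treated differently.
4. Extend SAP 7.11 to partial onset dates that could fall on either side of rescue, so that they do not default silently to pre-rescue.
5. Apply the same start-date rule to concomitant medications (SAP 7.9 and 11.2). They have no separate post-rescue summary, so a medication started before rescue but recorded at the rescue visit would appear only in the listings.

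The cost is SAP wording and one extra derivation. The plan already handles AE start dates (7.11) and a rescue date (14.3), so no new data are needed. The small downside is a few partial dates whose placement stays ambiguous.

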7.10 Missing Data Imputation for Efficacy Endpoints

The study primary endpoint is proportion of subjects having a ≥ 15 -letter improvement (3-line gain) from baseline in best-corrected visual acuity (BCVA) at Month 6. For the primary analysis, intercurrent events will be addressed using composite variable strategies. That is subjects who received any rescue surgeries prior to Month 6 or drop out the study due to any reasons prior to Month 6 will be imputed as treatment failure (i.e. not improve by ≥ 15 letters).

For the statistical analysis, the following two binary endpoints will be imputed using the same method as the primary endpoint:

- proportion of subjects having a ≥ 10 -letter improvement (2-line gain) from baseline in best-corrected visual acuity (BCVA) at Month 6
-

In addition, the following two continuous endpoints will be imputed using last observation carried forward (LOCF) for their statistical analyses:

- best-corrected visual acuity (BCVA)
- central corneal thickness (CCT)

7.11 Partial or Missing Date Handling

Partial or missing dates will be imputed when complete dates are required to flag data as treatment-emergent or concomitant with treatment.

Partial/missing start and end dates for AEs and concomitant medications will be imputed as follows.

Partial/missing start date:

- Dates with missing day only will be imputed as the 1st of the month unless the month and year are same as the month and year of first dose of study medication, in which case missing day will be imputed as the first dose day of study medication.
- Dates with both day and month missing will be imputed as 1 Jan unless the year is same as the year of first dose of study medication, in which case missing day and month will be imputed as the first dose day and month of study medication.
- Completely missing dates will be imputed as the first dose date of study medication unless the end date is on or before the first dose date of study medication, in which case missing date will be imputed as 1 Jan of the same year as the end date.

Partial/missing end date:

- Dates with missing day only will be imputed as the last day of the month.
- Dates with both day and month missing will be imputed as 31 Dec.
- If the ongoing flag is missing or “Yes” then the date will not be imputed unless death date is available, in which case the missing date will be imputed as the death date. If ongoing is “No” then the missing end date will be imputed as the last dose date.
- If the imputed date is after the date of death, then the end date will be set equal to the date of death.
- The original dates will be displayed in data listings and the imputed dates will be used in derivations only (study day, treatment-emergence status, etc.).

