11.2 Prior and Concomitant Medications

Prior and concomitant medications will be coded using the World Health Organization Drug Dictionary (WHODRUG) GLOBAL B3 September 1, 2023 and summarized by therapeutic drug class (Anatomical Therapeutic Chemical [ATC] 3 classification) and preferred name. Subjects are counted only once under each therapeutic class or preferred name (generic drug name) for which they have at least one concomitant medication. If the ATC3 classification is not provided, then the next lowest classification that is provided in the coding dictionary will be used.

Concomitant medications are medications which started 1) prior to initiation of study treatment administration and continuing for any period of time following the Day 1 administration of study treatment or 2) at any time following the Day 1 administration of study treatment. Prior medications are medications which are started before the Day 1 administration of study drug.

Ocular prior and concomitant medications will be summarized using discrete summary statistics and presented separately for study eye and non-study eye. Non-ocular prior and concomitant medications will be similarly summarized but at the subject level. For the concomitant summaries, any data collected at and after rescue visits will not be used.

Subject concomitant medications will be presented in separate listings for ocular and non-ocular data. The listings will indicate if medications are prior and/or concomitant medications.

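### SAP 7.11 moves partial start dates in the injection month or year to the injection date without checking the end date, so medications known to have stopped before injection are misclassified

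*SAP*

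**What the plan says.** SAP 7.11 sets out how incomplete dates are completed. Its stated trigger is: "Partial or missing dates will be imputed when complete dates are required to flag data as treatment-emergent or concomitant with treatment". Its scope is: "Partial/missing start and end dates for AEs and concomitant medications will be imputed as follows". There are three rules for start dates.

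- **Day missing.** Use the first of the month, except when month and year match the first dose, "in which case missing day will be imputed as the first dose day of study medication".
- **Day and month missing.** Use 1 January, except when the year matches the first dose, "in which case missing day and month will be imputed as the first dose day and month of study medication".
- **Completely missing.** Use the first dose date, "unless the end date is on or before the first dose date of study medication"; then use 1 January of the end-date year.

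Only the third rule mentions the end date. Nothing later in the section requires a start to precede its end; the only cap is the date of death, and it applies to end dates. Listings show the original dates, while "the imputed dates will be used in derivations only".

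SAP 11.2 supplies the definitions that use these dates: "Prior medications are medications which are started before the Day 1 administration of study drug". A medication is concomitant if it began earlier and continued past the injection, or if it began "at any time following the Day 1 administration of study treatment". This second limb has no end-date condition.

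**The concern.** Moving an uncertain start to the injection date is a sensible cautious default when the timing really is unknown. It is not sensible when the recorded end date already shows that the drug was stopped before injection. The SAP accepts this for a completely missing start but not for a partial one, so knowing more about the start gives a worse answer. Medications are recorded from the Screening Visit, up to 77 days before injection, so drugs that were stopped before surgery can be expected in the data.

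What is at stake is the accuracy of the prior and concomitant medication summaries, and of the study days and prior/concomitant flags derived from the same dates.

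**Working it through.** The plan states no figure on this point, so there is nothing to reproduce. The check applies the written rules to records.

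**Inputs.** The three start-date rules (SAP 7.11), the prior and concomitant definitions (SAP 11.2), the study-day formula (SAP 6.4) and 20 planned subjects per arm (SAP Table 1). The calendar dates are illustrative assumptions, with injection on 20 June 2024.

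| Recorded start | Recorded end | Imputed start | Start minus end | Prior? | Concomitant? |
|---|---|---|---|---|---|
| June 2024, day missing | 10 June 2024 | 20 June 2024 | 20 − 10 = 10 days | No | Depends on reading |
| 2024, day and month missing | 15 March 2024 | 20 June 2024 | 16 + 30 + 31 + 20 = 97 days | No | Depends on reading |
| Completely missing | 15 March 2024 | 1 January 2024 | Start precedes end | Yes | No |
| May 2024, day missing | 10 June 2024 | 1 May 2024 | Start precedes end | Yes | No |

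Rows two and three differ only in that the year of the start is known in row two. That extra information turns a correct classification into a wrong one.

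**The two readings.** An imputed start equals Day 1 and has no clock time. If a Day 1 start counts as following the injection, the drug in rows one and two is concomitant. This is the natural reading, because SAP 7.11 imputes to Day 1 in order to set that flag. If following means strictly after Day 1, the drug is neither prior nor concomitant and leaves both summaries. The correct class is prior only, so it is misclassified either way.

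**Study days.** In row one the end is Day −10 (10 June minus 20 June) and the start is Day 1 (20 June minus 20 June, plus 1). The derived start follows the derived end.

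**Is this peculiar to the chosen dates?** No. With injection date D and known end e before D, both partial-date rules set the start to D, so start minus end is D − e, which is always positive. Counting every pair of injection date and earlier end date in 2024:

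- same month: the sum of n(n − 1)/2 over months of n days is 7 × 465 + 4 × 435 + 406 = 5,401 pairs;
- same year: 366 × 365/2 = 66,795 pairs.

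All 5,401 and all 66,795 give a start after the end. With the end-date check added, none do, and all become prior only. These counts show that the rule fails whenever its conditions are met. They say nothing about how often that happens.

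**Partial end dates.** An end of May 2024 becomes 31 May, so a start of 2024 still lands 20 days after it (20 June minus 31 May). An end of June 2024 becomes 30 June, which hides the conflict.

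**Size in a table row.** One subject in an arm of 20 is 1/20 = 5 percentage points. SAP 11.2 counts a subject once per drug class or preferred name, so a row moves only if that subject has no other record in it. Five points per record is therefore a maximum.

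**The case against.** The strongest defence rests on the opening sentence of SAP 7.11: dates are completed only when a complete date is needed to set a flag. If the end is known to precede injection, the drug cannot be concomitant whatever its start, so no imputation is needed and the rule would never apply. This has some force, but the third rule undercuts it. That rule provides expressly for an end no later than the first dose, which would be pointless if such records were never imputed. A programmer following the text would impute them.

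A second defence is that concomitant status is not certain. That stands, as the two readings above show, but neither reading gives the right class.

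A third is that such records may be rare. That also stands. The documents give no look-back period for prior medications. With injection on 20 June 2024 the earliest screening date is 4 April, so whether a drug stopped on 15 March would be recorded depends on form instructions that are not in the documents. The 10 June example, ten days before injection, does not depend on a long look-back.

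A reader might also infer that a properly washed-out drug from Protocol Table 2 would be reported as a prohibited-medication deviation. The documents do not support that. SAP 9 draws deviations from a file that the sponsor reviews on an ongoing basis and does not say that imputed dates feed it. Listings keep the original dates, and the washouts are counted back from Screening. A drug stopped 30 days before a screening visit at least 7 days before injection ended at least 37 days before it, so it cannot fall in the injection month. Only the year-only rule could reach it, and an aggregate table row does not make anyone a deviator.

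**Conclusion.** The point holds. Two of the three start-date rules give an impossible start for any medication with a known end before injection and a partial start in the injection month or year. Such a record loses prior status and is misclassified. The text is wrong as written, and the SAP's own third rule shows the intended logic.

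The consequence is small. It is limited to the descriptive prior and concomitant medication summaries and to the study days and flags derived from the imputed dates. The number of affected records is unknown. The bound of 5 percentage points per record assumes an arm of 20 and no other record for that subject in the row. Original dates remain in the listings, so an error could be traced. Efficacy and deviation reporting are not shown to be affected. Nor are the adverse event tables, because Protocol 9.4.1 records events from Day 1. This is worth correcting but is not critical.

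**What to change.** In SAP 7.11, add to the first two start-date rules the condition already in the third. If the end date is no later than the first dose date, impute the first of the recorded month (day missing) or 1 January of the recorded year (day and month missing). Keep the third rule's tie handling, so that a drug ending on Day 1 is treated alike under all three. Add a general rule that no imputed start may fall after the end date, whether that end is recorded or itself imputed.

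One detail should be settled at the same time. SAP 7.11 also covers adverse events. An event with a partial start that ended on Day 1 would, under the added condition, be moved before injection and lose its treatment-emergent flag. Confining the added condition to medication records avoids this, and adverse events do not need it because they are recorded from Day 1.

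The cost is two clauses and one sentence in the SAP and a small change to the date program. Data collection does not change.

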8.4.1 Visit 1 (77 to 7 Days Prior to Day 1) Screening

- Informed Consent
- Demographics
- Medical/Surgical History
- Eligibility Review
- Uncorrected Visual Acuity (UCVA)
- BCVA (ETDRS) by Manifest Refraction (through phoropter) ([Appendix 2](#))

■ [REDACTED]

■ [REDACTED]

■ [REDACTED]

- SD-OCT (Macula)
- CCT by Ultrasonic Contact Pachymetry (Appendix 7)
- Slit Lamp Biomicroscopy
- Slit Lamp Photography
- Goldmann Tonometry (IOP) (Appendix 5)
- Gonioscopy (Appendix 6)
- Dilated Fundus Examination
- Prior/Concomitant Medications
- [REDACTED]
- Laboratory blood draw (hematology, chemistry) (samples to be sent to Central Lab)
- Urine Pregnancy Test (for women of childbearing potential)
- Cohort assignment

8.4.2 Visit 2 Procedure/Day 1

- Surgery/Study Treatment
- Adverse Events
- Prior Concomitant Medications

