9.4 Monitoring and Recording of AEs and SAEs

9.4.1 Adverse Events

Any AE experienced by the subject from Visit 2 (Day 1) through Visit 10 (Month 12) is to be recorded in the eCRF, regardless of the severity of the event or its relationship to study treatment.

Any AEs already documented at a previous assessment and designated as ongoing, should be reviewed at subsequent visits as necessary. If these have resolved, this should be documented.

Changes in intensity or frequency of AEs should be recorded as separate events (i.e., a new record started).

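### SAP 7.11's rule for completely missing start dates drops an undated adverse event that ended on Day 1 from the TEAE tables, and may deny prior status to undated screening drugs still in use after Day 1

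*SAP*

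**What the plan says.** SAP 7.11 applies one set of rules to two kinds of record: "Partial/missing start and end dates for AEs and concomitant medications will be imputed as follows". For a start date with no day, month or year, "Completely missing dates will be imputed as the first dose date of study medication unless the end date is on or before" that date. Where the exception applies, the start goes to the beginning of the year in which the record ended: "in which case missing date will be imputed as 1 Jan of the same year as the end date". Listings keep the original dates, and "the imputed dates will be used in derivations only (study day, treatment-emergence status, etc".

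The definitions that use these dates are elsewhere. SAP 11.2: "Prior medications are medications which are started before the Day 1 administration of study drug". SAP 14.1 counts an event as treatment-emergent if it occurs at or after the Day 1 injection, or was already present and worsens then.

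The two kinds of record are collected over different periods. "Prior/Concomitant Medications" is on the screening list in Protocol 8.4.1, 77 to 7 days before Day 1. Protocol 9.4.1 starts later for events: "Any AE experienced by the subject from Visit 2 (Day 1) through Visit 10 (Month 12) is to be recorded". The Schedule of Assessments likewise has no adverse event entry at screening.

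**The concern.** A rule that sends undated records to either the dose date or 1 January ought to respect what is already known about them. Here it does not in two situations.

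For adverse events, anything recorded as planned was present on or after the day of surgery. An event that ended that same day meets *on or before*, so it is dated to 1 January and treated as pre-treatment. The first two start-date bullets of 7.11 go the other way: when the known month or year matches that of the dose, they choose the dose date, which keeps an event treatment-emergent.

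For medications, a drug reported at Visit 1 was in use at least 7 days before injection. If its start is wholly unknown and it continued past Day 1, the rule starts it on the day of injection, which fails the SAP 11.2 definition of prior.

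At stake are the completeness of the treatment-emergent tables for the day of surgery, and the accuracy of the prior-medication counts and the prior flag in the listings.

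**Working it through.** The plan gives no figure to reproduce, so the check applies its rules literally.

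Inputs:
- D = first dose date. There is a single injection (Protocol 8.1), so D is also the last dose date.
- E = end date; S = imputed start. From SAP 7.11: S = D if E is later than D or the record is ongoing; S = 1 January of the year of E if E ≤ D.
- Prior: S < D (SAP 11.2). Treatment-emergent, without worsening: S ≥ D (SAP 14.1).
- D = 15 May 2024 is assumed, for illustration only.

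| Record, start wholly missing | E | S | Result |
|---|---|---|---|
| Drug, ongoing | none | 15 May | not prior |
| Drug, stopped after Day 1 | 25 May | 15 May | not prior |
| Drug, stopped on Day 1 | 15 May | 1 January | prior |
| Drug, stopped before Day 1 | 10 May | 1 January | prior |
| AE, ended Day 1 | 15 May | 1 January | not treatment-emergent |
| AE, ended Day 2 | 16 May | 15 May | treatment-emergent |
| AE, ongoing | none | 15 May | treatment-emergent |

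The AE that ended on Day 1 gets study day −135 under SAP 6.4 (31 + 29 + 31 + 30 + 14 = 135 days). An event that ended one day later, with the same ignorance of its start, is treatment-emergent.

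Over all 366 possible injection dates in 2024:
- The Day 1 AE loses treatment-emergent status on 365 dates (all but 1 January).
- Its imputed onset lies 0 to 365 days before injection, on average 365/2 = 182.5 days. The gap exceeds 77 days on 366 − 78 = 288 dates (288/366 = 79%), which puts onset ahead of the whole screening window.
- The ongoing drug is not prior on 366 of 366 dates.

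These counts describe how the rule behaves, not how often such records will occur.

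Which AEs can reach the exception? One with a known end date, recorded within the Protocol 9.4.1 window, cannot have E < D. So only E = D qualifies, and for AEs collected as planned the exception catches Day 1 events alone.

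Two neighbouring cases in 7.11:
- An AE with both dates missing and marked not ongoing gets E = last dose date = D. If the end is imputed first, S = 1 January and it is not treatment-emergent; if the start is imputed first, S = D and it is. The order is not stated.
- A start known only to the injection month and year, or only to the injection year, also becomes D. A screening drug with such a date is not prior either. These bullets have no end-date check, so a drug with a year-only start that stopped earlier in the injection year would get a start after its end.

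Size for one AE: 1/20 = 5 percentage points of an arm, if that subject has no other treatment-emergent event with the same term.

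**The case against.** The medication half depends on a reading. SAP 7.11 opens with "Partial or missing dates will be imputed when complete dates are required to flag data as treatment-emergent or concomitant with treatment", which does not name the prior flag, and a drug reported at Visit 1 needs no complete date to be known as prior. This stands: the misclassification is conditional. The open-ended list of derivations later in the section leaves the other reading possible. If imputed dates do not feed the flag, 7.11 gives no rule for the prior status of an undated drug, so a sentence is needed either way.

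For AEs, the *on or before* branch has a purpose. SAP 14.1 provides for events continuing from screening, and one of those that ended on Day 1 without worsening is not treatment-emergent. Day 1 also includes anesthesia, incision and polishing before the injection, so a Day 1 end date does not prove onset after it. Both points are fair. They show that the status is uncertain, but dating the event to 1 January settles the doubt by exclusion. For AEs that are ongoing or ended later, the rule already errs towards inclusion.

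Two stronger readings are tempting. A reader might infer that screening drugs in general lose prior status; those that ended on or before Day 1 take the 1 January branch and keep it. A reader might also infer that a restricted drug in use before screening would escape notice as a washout breach. The documents do not support that: breaches come to light through the Visit 1 eligibility review and the sponsor's ongoing deviation review (SAP 9), nothing ties deviations to imputed starts, and the listings show the blank date.

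**Conclusion.** The point holds in narrow form. The AE half is wrong as written: an undated event that ended on Day 1 leaves the treatment-emergent tables, though not the AE listing. The medication half holds if imputed dates are used for the prior flag. It then affects only drugs with a wholly missing start that were ongoing or stopped after Day 1, plus those with a partial date in the injection month or year. All of these that continued past Day 1 remain in the concomitant summaries.

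The size is small. An event that resolved on the day of surgery with no start date at all should be very rare. The number of drug records cannot be estimated, because the documents give neither a missing-date rate nor a count of drugs per subject. SAP 11.2 also counts each subject once per class or name, so a count of records would overstate the effect on the tables. No efficacy result changes. This is a low-priority correction, worth making because the logic is faulty and the repair is short.

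**What to change.** In SAP 7.11, separate the two kinds of record.

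- Adverse events: change *on or before* to *before*, so that an undated event that ended on Day 1 is imputed to Day 1 and counted as treatment-emergent. Add that an imputed end date does not trigger the exception, so the result for a fully undated event does not depend on which date is imputed first.
- Medications: state that a drug reported in use at the Screening Visit is flagged as prior, and also as concomitant if it continued past Day 1, whatever start date is imputed. Apply the same to partial start dates in the injection month or year.

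The cost is one word, two or three sentences and a small programming change, with no additional data collection intended. The documents do not describe the medication form, so the sponsor should confirm that it identifies which drugs were reported at screening.
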